2.5 Sub group analyses

If sufficient number of patients and transfusions are included, transfusion regimen in different subpopulations will be analysed:

- Patients >75 years
- Patients with acute coronary syndrome
- Patients with cardiovascular diseases other than acute coronary syndrome
- Patients post cardiothoracic surgery
- Patients with traumatic brain injury
- Patients with septic shock
- Haematology patients
- Oncology patients
- Patients with ARDS
- Patients on ECMO

3. METHODS

3.1 Study parameters/endpoints

3.1.1 Main study parameter/endpoint

Main study aim is to describe current transfusion practice. This includes number of transfused units of red blood cells concentrates, platelet concentrates, plasma, cryoprecipitate when available and products that are not blood components but that derived from blood and that include coagulations factors such as prothrombin complex, fibrinogen or tranexamic acid per patient. This will be correlated with haemoglobin levels, platelet count, INR (or PT), fibrinogen prior to transfusion.

3.1.2 Secondary study parameters/endpoints

Secondary parameters will be:

- Mortality and length of stay in the ICU.
- Differences of transfusion regimes between world regions
- Differences of transfusion practices between different patient subgroups

3.2 Data collection

All newly admitted patients at the ICU older than 18 years will be included for seven consecutive days. At the start, baseline characteristics will be scored prospectively. Also, patients will be scored daily using daily questionnaires until discharge with a maximum of 28 days. At the day 28, patient outcomes are scored irrespective whether they were discharged. Furthermore, for each transfusion event or administration of coagulations factors a questionnaire will be filled in. See Figure 1 for the workflow.

Figure 1. Workflow InPUT study

The following data will be collected:

Baseline characteristics:

- Demographics
- SOFA score at inclusion
- Type of admission
- Presence or absence and the type of shock on the study day
- Heart rate, systolic and diastolic blood pressure
- Ventilator settings
- Renal replacement therapy during that day

Questionnaire per transfusion event:

- General
 - \circ Active bleeding
 - Bleeding control
 - Red cell transfusion
 - Haemoglobin(Hb)/haematocrit (Ht) level
 - Hb threshold for this patient
 - Presence of physiological trigger, and which trigger has been used.
 - Transfusion relevant comorbidity

- Number of units transfused
- Origin of transfusion product (e.g. allogeneic, autologous, cell salvaged blood)
- Platelet transfusion
 - Platelet count prior to transfusion
 - Platelet count threshold for transfusion for this patient
 - Type of Platelet concentrate
 - Anticoagulant usage the past 72 hours
 - Usage of point of care to assess blood coagulation: ROTEM or multiplate
 - Number of units transfused
 - Upcoming procedures
- Plasma
 - INR prior to transfusion
 - $_{\odot}$ Anticoagulant usage the past 72 hours
 - Usage of point of care to assess blood coagulation
 - Amount of plasma transfused
 - Upcoming procedures
- Prothrombin complex concentrate (i.e. Cofact ®).
 - o INR or PT
 - Dosage of prothrombin complex concentrate
 - Usage of point of care to assess blood coagulation
 - Upcoming procedures
- Massive transfusion protocol:
 - Lowest haemoglobin level
 - Lowest platelet count
 - o INR
 - Usage of point of care to assess blood coagulation
 - Number of Red blood cell units transfused
 - Number of platelet concentrate units transfused
 - Amount of plasma transfused
 - Tranexamic acid, fibrinogen, rFactor VIIa, Cryoprecipitate, factor XIII, apropitin, novoseven (=eptacog alfa)
 - Bleeding control

Daily questionnaire

- Estimated blood loss
- Total number of transfused RBCs

- Total number of transfused platelet concentrates
- Total ml transfused plasma
- Volume administration in 24 hours
- Lowest haemoglobin level, lowest platelet count, highest INR in 24 hours
- Tranexamic acid administration in 24 hours
- Transfusion within 24 hours outside the ICU (e.g. on operating theatre)

At day 28

- 28-day mortality
- Length of stay on ICU
- Iron administration within ICU admission

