1.2 Relevance

Transfusion practice has already been studied before on the ICU and the operating theater^{17,19–21}. However, these studies were held in a limited number of hospitals within the same country, were limited to only one type of transfusion, are often outdated and difficult generalizable to other hospitals and regions. Since these large observational studies, numerous of randomized controlled trials on RBC transfusion have been published supporting the safety of more restrictive transfusion strategy^{7–10}. However, current

InPUT-study Protocol, dated 09-09-2020

transfusion practice remains unknown. There is a need 1) to describe current transfusion practice for RBC but also for other blood components and coagulation factors, 2) to identify area of improvement, 3) to have large observational data to generate hypotheses on optimal transfusion triggers in subgroups of critically ill patients including patients with brain injury, cardiovascular diseases and elderly patients.

This study will be the first worldwide transfusion practice point prevalence trial on the ICU, which studies the practice of administration of different blood products and coagulation factors.

OBJECTIVES

Primary Objective:

- Number of red blood cell, platelet, and coagulation factors in correlation to haemoglobin levels, platelet count and INR (or PT) respectively.

Secondary Objectives:

- To evaluate which other triggers such as hemodynamic or comorbidities influence RBC transfusion practice.
- To compare haemoglobin levels in transfused patients with nadir levels of haemoglobin in non-transfused patients
- To compare platelet count in transfused patients with platelet to nadir platelet count in non-transfused patients
- To compare INR (or PT) in transfused patients with plasma to nadir level of INR(PT) in non-transfused patients
- To compare transfusion practice between different subgroups of patients including shock septic, haematology, cardiovascular disease without acute coronary diseases and coronary disease
- Association between restrictive and liberal RBC transfusion strategy on ICU length of stay and 28-day mortality
- Association between restrictive and liberal platelet transfusion strategy on ICU length of stay and 28-day mortality
- Association between restrictive and liberal coagulation factor suppletion strategy on ICU length of stay and 28-day mortality

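### The massive-transfusion form records the lowest haemoglobin and platelet count, not the pre-transfusion values that the main endpoint names

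*Protocol*

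**What the plan says.** Protocol section 3.1.1 defines the main endpoint as the number of units of each product per patient and adds: "This will be correlated with haemoglobin levels, platelet count, INR (or PT), fibrinogen prior to transfusion". The primary objective (Objectives, after section 1.2) describes the same relation without a sampling time: "Number of red blood cell, platelet, and coagulation factors in correlation to haemoglobin levels, platelet count and INR (or PT) respectively".

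Section 3.2 lists the items collected at each transfusion event:

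- **Platelets:** "Platelet count prior to transfusion". The plasma section fixes the time of its INR in the same way.
- **Red cells:** "Haemoglobin(Hb)/haematocrit (Ht) level", with no time stated, followed directly by "Hb threshold for this patient".
- **Prothrombin complex concentrate:** an INR or PT, with no time stated.
- **Massive transfusion:** "Lowest haemoglobin level", "Lowest platelet count" and an INR with no time stated, on the same form as "Number of Red blood cell units transfused" and the totals of other products.

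The daily questionnaire, also in section 3.2, asks for the lowest haemoglobin, the lowest platelet count and the highest INR over 24 hours.

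**The concern.** The endpoint describes what the laboratory value was when clinicians gave blood. On the massive-transfusion form, the haemoglobin and platelet items are a different quantity. During heavy bleeding the lowest value can occur after the first units, through continuing loss or dilution by what has been given. It is then partly a consequence of the episode rather than the value on which the episode began.

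If such a value were used as the pre-transfusion value beside the episode's unit total, low values and high unit counts would tend to go together, whatever prompted the transfusion. Section 5.2 also leaves the criteria for liberal and restrictive regimes to be set during the study. If those criteria draw on recorded laboratory values, the mistimed values would carry into the mortality and length-of-stay comparisons.

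**Working it through.** The point is a comparison of definitions, so the endpoint is set against each listed source of the laboratory value.

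| Source in section 3.2 | Laboratory item | Value before transfusion? |
|---|---|---|
| Platelet section | Platelet count | Yes, stated |
| Plasma section | INR | Yes, stated |
| Red cell section | Hb/Ht | Not stated; context suggests it |
| Prothrombin complex section | INR or PT | Not stated |
| Massive-transfusion section | Lowest Hb, lowest platelets, INR | No for Hb and platelets; INR not stated |
| Daily questionnaire | 24-hour extremes | No |

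**Step 1. Can the lowest value stand in for the pre-transfusion value?** The form gives no window. If the window covers the whole episode and includes the pre-transfusion sample, the lowest value is at or below that sample. The two are equal only when no later sample is lower. If the window opens with the first unit, the pre-transfusion sample is not in it at all. In neither case is the recorded item the one in section 3.1.1.

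**Step 2. Can another listed item supply it?** The daily questionnaire cannot, since a 24-hour extreme has the same defect. The product-specific sections could, but only if they are also completed for massive transfusions. Section 3.2 requires a questionnaire for each transfusion event and does not say whether the massive-transfusion section replaces the product sections or is added to them.

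**Step 3. Can the size be worked out?** The only relevant figures are in section 2.4, and they reproduce: 10,000 × 0.10 = 1,000 and 10,000 × 0.20 = 2,000 transfusion events. The protocol gives no share of massive transfusions and no units per event. With a share m, u units per massive event and v units per other event, the fraction of units affected is m·u / (m·u + (1 − m)·v). Two sets of purely assumed inputs show how far the answer depends on them:

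- m = 1%, u = 6, v = 1.5: 0.06 / (0.06 + 1.485) = 3.9%
- m = 5%, u = 10, v = 1.5: 0.50 / (0.50 + 1.425) = 26.0%

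A range of about 4% to 26% reflects the assumptions, not the trial. The formula also treats all events as if they used one type of unit, whereas the protocol's events include platelets, plasma and coagulation factors. No figure is put forward as a result.

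**The case against.** Several arguments on the other side have force.

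- **Section 3.2 is a summary list.** Section 3.7 says that an electronic CRF is used, and it is not shown. It may define sampling times. This stands as a limit on what can be concluded about the instrument. It does not explain why the list asks for a lowest value where the endpoint needs a prior one.
- **The lowest value may be deliberate.** In massive bleeding the decision may rest on the bleeding and not on a laboratory trigger, and the lowest value describes severity. That is a good reason to keep the item. Section 3.1.1, however, makes no exception for these events.
- **The primary analysis is descriptive (section 5.1).** No test or effect estimate is biased. This limits the severity, but a description still needs the variable it describes.

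A reader might infer more than the protocol supports:

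- **That red cell haemoglobin may be a post-transfusion value.** The item stands beside the patient's threshold and the physiological trigger, in a questionnaire that section 2 says concerns prescribing. Section 3.1.1 supplies the intended timing. For red cells and prothrombin complex this is unclear labelling, no more.
- **That the endpoint cannot be derived for massive transfusions.** The product sections may also be completed, and the protocol is silent on this.
- **That lowest and pre-transfusion values will be pooled.** No section says so, and a separate form could equally point to separate handling. The analysis plan, where such a rule would normally sit, is not at hand.
- **That these events carry most of the units.** The name makes high unit counts plausible, but the protocol gives no figure.

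**Conclusion.** The mismatch is real and confined to one form. Section 3.1.1 needs values from before transfusion. The massive-transfusion section lists the lowest haemoglobin and platelet count and an untimed INR, and no other listed item clearly fills the gap. An analysis plan can decide how to use a value, but it cannot supply one that was not recorded, so the remedy belongs in data collection.

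The conclusion assumes that section 3.2 reflects what the CRF asks, and that the product sections are not routinely completed as well for massive transfusions. If either assumption is wrong, a clarifying sentence in section 3.2 would be enough. The number of units affected is unknown. The change is worth making because the laboratory value is the central variable of the main endpoint, but nothing here invalidates the study.

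**What to change.** 1. On the massive-transfusion form, add the last haemoglobin, platelet count and INR or PT before the first unit of the episode, using the timing words that the platelet and plasma items already carry.
2. Keep the lowest haemoglobin and platelet count as separate severity items. State that they are not used as the pre-transfusion value in the description of units by trigger.
3. State in section 3.2 whether the product-specific sections are also completed for massive transfusions.
4. As a minor clarification, label the red cell Hb/Ht item and the prothrombin complex INR or PT item as values before transfusion.

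The cost is a few extra fields for massive-transfusion events, two relabelled items and one or two sentences. The study uses routine-care data, so where these values were measured they should be in the clinical record. The timeline in section 8 puts the start of data collection in March 2020 and this protocol is dated 09-09-2020. Centres that have already completed their week would have to enter the added values from their records.

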3.3 Withdrawal of individual subjects

Apart from withdrawal of consent, subjects will not be withdrawn from the trial. In case of withdrawal, the data collection will be stopped and subject will not be replaced.

3.4 Replacement of individual subjects after withdrawal

Subjects will not be replaced in case of withdrawal.

3.5 Follow-up of subjects withdrawn from treatment

Not applicable

3.6 Premature termination of the study

Since this is an observational study, no interim analysis is planned. Therefore there are no criteria that are defined for premature termination of the study.

3.7 Feasibility

The feasibility of this protocol was shown in a pilot study. Based on this pilot, the protocol was adjusted. Time consuming data collection that did not result in reliable and useful information was removed from the study protocol, including daily fluid balance and additional questions for the non-transfused patients. Also the workflow of the data collection was improved using an electronic CRF. We expect this to reduce the amount of time to complete the different forms. Also obtaining informed consent will not be necessary in every centre depending on national and local regulations for observational research.

4. SAFETY REPORTING

4.1 Temporary halt for reasons of subject safety

In accordance to section 10, subsection 4, of the WMO, the sponsor will suspend the study if there is sufficient ground that continuation of the study will jeopardise subject health or safety. The sponsor will notify the accredited METC without undue delay of a temporary halt including the reason for such an action. The study will be suspended pending a further positive decision by the accredited METC. The investigator will take care that all subjects are kept informed.

5. STATISTICAL ANALYSIS

5.1 Primary study parameter(s)

This is a descriptive study. Only descriptive statistical methods will be used for the primary endpoint. Continuous normally distributed variables will be expressed by their mean and standard deviation or when not normally distributed as medians and their interquartile ranges. Categorical variables will be expressed as n (%).

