2. STUDY DESIGN

This study is a prospective, descriptive study and only includes objective data collected as part of routine care. No intervention takes place. ICUs in different world regions will be asked to participate in this study. Each centre can choose a week to participate from several pre-specified weeks. All newly admitted patients on the ICU in that specific week will be included and followed until discharge and/or 28 days (see Figure 1 for study flow).

A transfusion event is defined as the administration of a blood derived product or coagulation factor with as aim to treat or prevent anaemia, bleeding and/or coagulopathy. This includes administration of red cell concentrates, platelet concentrates, plasma and coagulation factors including fibrinogen concentrate, cryoprecipitate and prothrombin complex. For each transfusion event data will be collected prospectively using a questionnaire on prescription behaviour. Also transfusions administered on the operating theatre while admitted to the ICU will be included for analysis.

The daily questionnaire contains clinical an laboratory data. These data include nadir haemoglobin levels, platelet count and INR or PT. This data will be necessary to compare data between patients who did receive a transfusion to patients who did not receive transfusions. Furthermore, information about 24h fluid balance and anticoagulants administration will be collected. Finally after 28 days patient outcome data: length of ICU stay and 28-day mortality will be collected.

STUDY POPULATION

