2.4 Sample size calculation

It is planned to recruit 10 000 patients. The CRIT study and European data reported RBC transfusion rate of 30 to 40% for patients during their stay on the ICU. Furthermore transfusion rates for platelet concentrates and plasma of 12% and 9% have been reported^{17,22}. However, in this study we will include all transfusion events during a prespecified week and day. Depending on the study design, it is estimated that approximately 10-20% of all patients will receive at least one blood product, resulting in a total of approximately 1000-2000 transfusion events. As for the primary outcome merely descriptive statistics will be used, this will be a sufficient number of transfusion events. This is in accordance with data available from the most recent study investigating transfusion practices worldwide, in which 10.069 patients were included¹⁹.

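### The primary endpoint is to be related to a fibrinogen level that no listed form records; tranexamic acid and the denominator for units per patient also need to be settled

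*Protocol*

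**What the plan says.** **Endpoint.** Protocol section 3.1.1 counts units of each product per patient and ties the count to laboratory values: "This will be correlated with haemoglobin levels, platelet count, INR (or PT), fibrinogen prior to transfusion". It adds a group of products that come from blood without being blood components, with examples "such as prothrombin complex, fibrinogen or tranexamic acid per patient".

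**Transfusion event.** Section 2 (Study design) says: "A transfusion event is defined as the administration of a blood derived product or coagulation factor". Its list covers red cells, platelets, plasma, fibrinogen concentrate, cryoprecipitate and prothrombin complex, and each event is to have a questionnaire. Tranexamic acid is not on the list.

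**Summary statistics.** Section 5.1 limits the primary endpoint to descriptive methods: "Continuous normally distributed variables will be expressed by their mean and standard deviation or when not normally distributed as medians and their interquartile ranges". For categorical data it gives counts and percentages. It does not say whether units are summarised over all patients, transfused patients or events.

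**Expected rates.** Section 2.4 states "It is planned to recruit 10 000 patients". On the share transfused, it says "it is estimated that approximately 10-20% of all patients will receive at least one blood product". From this it derives a yield of 1000 to 2000 events. It cites a red cell rate of 30 to 40% over the ICU stay, and says "transfusion rates for platelet concentrates and plasma of 12% and 9% have been reported".

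**The concern.** A primary correlate must be collected to be analysed. If the fibrinogen level is missing from the case report form, the fibrinogen part of the primary description is empty. If fibrinogen concentrate and cryoprecipitate have no block of their own, their use outside massive transfusion is an event by definition but leaves no recorded amount.

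The other two matters concern what is counted and over whom. Tranexamic acid belongs to the endpoint under one section and is absent from the event list in another. And a count that is zero for most patients is not normally distributed, so section 5.1 leads to median and IQR. If these are taken over everyone admitted, they can be zero throughout and say nothing about practice for that product.

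**Working it through.** **1. Endpoint against forms.** What section 3.2 lists:

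| Block | Laboratory value | Product amount |
|---|---|---|
| Red cells | Haemoglobin or haematocrit | Units |
| Platelets | Platelet count | Units |
| Plasma | INR | Amount |
| Prothrombin complex | INR or PT | Dosage |
| Massive transfusion | Lowest haemoglobin, lowest platelet count, INR | Red cell and platelet units, plasma amount; fibrinogen, cryoprecipitate, tranexamic acid and others named as agents |
| Daily form | Lowest haemoglobin, lowest platelet count, highest INR | Red cells, platelets, plasma; tranexamic acid on its own line |
| Fibrinogen or cryoprecipitate outside massive transfusion | None listed | None listed |

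Of the four correlates in section 3.1.1 (haemoglobin, platelet count, INR or PT, fibrinogen), three appear on the forms. The one mention of fibrinogen is as an agent given, not as a laboratory value. The Summary says fibrinogen as a product will be recorded by amount and type; the forms give no place for this outside massive transfusion.

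**2. Tranexamic acid.** Section 3.1.1 puts it among products derived from blood and counted per patient. Section 2's list leaves it out. The daily form records its administration separately, so the data for separate reporting exist.

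**3. Denominator.** The plan's own figure first: 10,000 × 0.10 = 1000 and 10,000 × 0.20 = 2000, which reproduces the stated range. This counts transfused patients, so it is a minimum for events.

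Let p be the share of patients who receive a product. The share with zero units is 1 − p. If 1 − p > 0.75, the 25th, 50th and 75th percentiles over all patients are all 0, however many units the transfused patients receive. If 1 − p lies between 0.50 and 0.75, the median is 0 and the upper quartile is at least 1.

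| Product | p | 1 − p | Median (IQR), all patients |
|---|---|---|---|
| Any, lower | 0.10 | 0.90 | 0 (0 to 0) |
| Any, upper | 0.20 | 0.80 | 0 (0 to 0) |
| Platelets | 0.12 | 0.88 | 0 (0 to 0) |
| Plasma | 0.09 | 0.91 | 0 (0 to 0) |
| Red cells, lower | 0.30 | 0.70 | 0 (0 to 1) up to 0 (0 to 2) |
| Red cells, upper | 0.40 | 0.60 | 0 (0 to 1) up to 0 (0 to 3) |

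The exact upper quartile for red cells needs the units per transfused patient, which the protocol does not give. The ranges assume a mean of 1.5 to 4 units, distributed as 1 + Poisson.

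**4. What the alternative would show.** For a proportion, the 95% half-width is 1.96 × √(p(1 − p)/10,000): 0.59 percentage points at 10%, 0.78 at 20%, 0.64 at 12% and 0.56 at 9%. These ignore clustering by ICU and would widen if practice is similar within units. Under the same assumed means, the median among transfused patients is 1 to 4 units.

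**The case against.** **Fibrinogen.** It can be called one stray word. The primary objective names only haemoglobin, platelet count and INR or PT, and the Summary's trigger list does not include fibrinogen. That makes deletion a reasonable remedy. It does not remove the contradiction, because section 3.1.1 is where the main endpoint is defined, and the missing event block remains.

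**Denominator.** A reader might infer that the whole primary result will be an uninformative 0 (0 to 0). The documents do not support that. Section 5.1 fixes no denominator and allows counts and percentages. The event form records units beside the pre-transfusion value, so a summary among transfused patients or per event is a natural reading. An analysis plan that is not shown may settle it. Nor does 0 (0 to 0) hold for red cells at 30-40%. That whole-stay rate may be the relevant one, since section 3.2 follows patients to discharge or day 28, although section 2.4 reasons from a week and day. What stands is that the text permits an empty summary for some products and should exclude it.

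**Tranexamic acid.** It would be too strong to say that it is counted as a blood component; section 3.1.1 says these products are not. No pooled total across products is specified either, so a distorted overall count is not shown. The mismatch between the two sections stands.

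**Length of stay.** A reader might infer that comparisons between regions are biased because a count per patient rises with time in the ICU. Follow-up time does vary. But the documents give no regional lengths of stay or daily transfusion rates, so no size can be put on this. Units per patient is a legitimate description, and a rate per ICU-day can be derived from data already collected for red cells, platelets and plasma.

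**Conclusion.** The fibrinogen contradiction holds in full. One of four stated primary correlates is on no listed form, and fibrinogen concentrate and cryoprecipitate have no event block outside massive transfusion. This rests on the lists in section 3.2 being complete, and no later analysis plan can repair it. The tranexamic acid mismatch between sections 2 and 3.1.1 holds as a matter of definition.

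The denominator point holds as a needed clarification, not as proof that the endpoint fails. Over all patients, the quartiles are all zero at the planning rates for any product, platelets and plasma. For red cells at the cited whole-stay rate, only the median and lower quartile are zero. A time base is a useful option, and its absence is not an error.

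**What to change.** 1. Add a short fibrinogen and cryoprecipitate block to the event form (level before administration, amount given), or delete fibrinogen as a correlate from section 3.1.1. The cost is a few fields in the electronic form, or one word. The protocol is dated 09-09-2020 and its timeline starts data collection in March 2020. If collection had begun, a new block would cover only later patients, and the report should say so.
2. Make sections 2 and 3.1.1 agree on tranexamic acid and report it separately as n (%), which the daily form already supports.
3. In section 5.1, state for each product: the proportion of patients transfused, with a 95% confidence interval that allows for clustering by ICU; and, among transfused patients, the median (IQR) of units and of the pre-transfusion value. This is a few lines of wording.
4. Optionally, give units per 100 ICU-days for red cells, platelets and plasma when regions are compared, because follow-up time varies. The daily totals and ICU length of stay supply it, so nothing new is collected.
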